9.4.4 Vital signs

Vital signs data will be summarized by treatment together with changes from baseline, where baseline is defined as the Day 1 predose assessment. Figures of mean vital signs and mean changes from baseline profiles will be presented by treatment.

Values for individual subjects will be listed.

9.4.5 Electrocardiogram (ECG)

ECGs will be performed for safety monitoring purposes only and will not be presented. Any clinically significant findings from ECGs will be reported as an AE.

9.4.6 Hepatic Monitoring

If a subject experiences elevated alanine aminotransferase (ALT) $\geq 3 \times$ upper limit of normal (ULN), alkaline phosphatase (ALP) $\geq 2 \times$ ULN, or elevated total bilirubin (TBL) $\geq 2 \times$ ULN, liver tests will be performed to confirm the abnormality. Additional safety data may be collected if required, as defined in the protocol. Where applicable, the following will be presented.

The subjects' liver disease history and associated person liver disease history data will be listed. Any concomitant medications that have potential for hepatotoxicity, including acetaminophen will be listed. Results from any hepatic monitoring procedures, such as a magnetic resonance elastography (MRE) scan, and biopsy assessments will be listed, if performed.

Hepatic risk factor assessment data will be listed. Liver related signs and symptoms data will be summarized by treatment and listed. Alcohol and recreational drug use data will also be listed.

All hepatic chemistry, hematology, coagulation, and serology data will be listed. Values outside the reference ranges will be flagged on the individual subject data listings.

9.4.7 Immunogenicity Assessments

The frequency and percentage of subjects with pre-existing antidrug antibody (ADA) and with treatment-emergent ADAs (TE ADA) to LY3478006 will be tabulated and listed.

For subjects who are ADA negative at baseline, TE ADAs are defined as those with a titer 2-fold (1 dilution) greater than the minimum required dilution of the assay. For subjects who are ADA positive at baseline, TE ADAs are defined as those with a 4-fold (2 dilution) increase in titer compared to baseline. The frequency and percentage of subjects with cross-reactive and neutralizing antibodies, if measured, may also be tabulated for subjects with TE ADA.

The relationship between the presence of antibodies and the PK parameters may be assessed.

Eli Lilly is responsible for the immunogenicity reporting of data.

9.4.8 Allergic/Hypersensitivity reactions

For all allergic and drug hypersensitivity reactions that occur, additional follow-up data will be collected to assess the patient's medical history, alternative causes, and symptoms. These data will be listed.

9.4.9 Injection/Infusion Site Reactions

Injection-site reaction data will be listed and summarized by ethnicity (overall, Japanese and non-Japanese) and treatment in frequency tables. The reaction data may include erythema, induration, pain, pruritus, and edema.

9.4.10 Neurological Examinations

New or worsened abnormality on the neurologic exam should be reported as an AE and listed. Neurological examination data will be listed for all subjects by treatment and timepoint.

9.4.11 Pupillometry Assessments

Pupillometry data will be listed for all subjects by treatment and timepoint.

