**Statistical Analysis:**

Summary statistics data tabulations and data graphs by ethnicity (Japanese and non-Japanese) will be provided as appropriate.

Adverse events will be listed, and if the frequency of events allows, safety data will be summarized using descriptive methodology. The incidence of symptoms for each treatment will be presented by severity and by association with the study drug as perceived by the investigator. The number of IP-related SAEs will be reported. Safety parameters, including safety laboratory, vital signs, neurologic examination, and pupillometry, will be listed and summarized using standard descriptive statistics.

Pharmacokinetic parameters for LY3478006 will be calculated by standard noncompartmental methods of analysis (NCA). The primary parameters for analysis will be  $C_{max}$  and  $AUC_{0-\infty}$ . Pharmacokinetic parameter estimates from the NCA will be evaluated to delineate effects of dose proportionality. Log-transformed  $C_{max}$  and  $AUC$  estimates will be evaluated in a linear model with log-transformed IV dose for healthy subjects as explanatory variable. The treatment differences will be back-transformed to present the ratios of geometric means and the corresponding 90% confidence intervals. For the SC dose, the bioavailability relative to IV infusion at the same dose will be evaluated via a log-transformed model.

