### 3.3. Benefit/Risk Assessment

There is no anticipated therapeutic benefit for subjects in this study.

Two safety topics emerged during the development of anti-NGF antibodies: atrophy of sympathetic neurons in animal studies, and an increased incidence of rapidly progressing osteoarthritis (RPOA) in human clinical trials. Sympathetic neuronal atrophy was not associated with demonstrable deficits in sympathetic function, and recovered with drug washout in adult animals (Angeletti et al. 1971; Bjerre et al. 1975; Belanger et al. 2017). Further, no major effects on sympathetic function have been reported in clinical trials to date in patients dosed with tanezumab (Brown et al. 2014; Brown et al. 2015) or in tanezumab-treated monkeys subjected to head-up tilt challenge (Belanger et al. 2017). In nonclinical repeat dose studies in rats (1-month) and non-human primates (3 months) minimal neuronal hypertrophy rather than atrophy was observed with LY3478006. No neuronal necrosis clinical sequelae were observed. Given the potential for compounds acting along this pathway to affect sympathetic function, this study will monitor for evidence of sub-clinical effects on autonomic function using pupillometry, which has been shown to detect dysfunction of both sympathetic and parasympathetic systems (Ferrari et al. 2010; Muppudi et al. 2013). While the likely mechanisms are unknown, RPOA in humans remains a potential risk for anti-TrkA inhibitors.

The nonclinical safety information for LY3478006 adequately supports the transition from preclinical status to a clinical, single-dose study. LY3478006 has not been administered to humans previously, thus the study is designed to be conducted in accordance with principles outlined in the Guideline on Strategies to Identify and Mitigate Risks for First-in-Human Clinical Trials with Investigational Medicinal Products (EMA 2017). Any identified risks are considered to be monitorable and manageable at the planned single ascending dose range of 10 mg to 1000 mg for LY3478006 in healthy subjects.

More information about the known and expected benefits, risks, serious adverse events (SAEs) and reasonably anticipated adverse events (AEs) of LY3478006 are to be found in the Investigator's Brochure (IB).

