### **10.3.1.2. Statistical Evaluation of Safety**

Safety parameters that will be assessed include safety laboratory, vital signs, neurologic examination, and pupillometry. The parameters will be listed, and summarized using standard descriptive statistics. Electrocardiogram and physical examination will be performed for safety monitoring purposes and will not be listed or summarized. Additional analysis will be performed if warranted upon review of the data.

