3. INTRODUCTION

This SAP has been developed after review of the Clinical Study Protocol (final version dated 04 November 2019).

This SAP describes the planned analysis of the safety, tolerability and pharmacokinetic (PK) data from this study. A detailed description of the planned TFLs to be presented in the clinical study report (CSR) is provided in the accompanying TFL shell document.

The intent of this document is to provide guidance for the statistical and PK analyses of data. In general, the analyses are based on information from the protocol, unless they have been modified by agreement with Eli Lilly and Company. A limited amount of information concerning this study (e.g., objectives, study design) is given to help the reader's interpretation. When the SAP and TFL shells are agreed upon and finalized, they will serve as the template for this study's CSR.

This SAP supersedes the statistical considerations identified in the protocol; where considerations are substantially different, they will be so identified. If additional analyses are required to supplement the planned analyses described in this SAP, they may be performed and will be identified in the CSR. Any substantial deviations from this SAP will be agreed upon with Eli Lilly and Company and identified in the CSR. Any minor deviations from the TFLs may not be documented in the CSR.

This SAP is written with consideration of the recommendations outlined in the International Conference on Harmonisation (ICH) E9 Guideline entitled Guidance for Industry: Statistical Principles for Clinical Trials¹ and the ICH E3 Guideline entitled Guidance for Industry: Structure and Content of Clinical Study Reports².

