9. STATISTICAL METHODOLOGY

9.1 General

Summary statistics and figures by ethnicity (Japanese and non-Japanese) will be provided as appropriate.

Data listings will be provided for all data that is databased. Summary statistics and statistical analysis will only be presented for data where detailed in this SAP. For continuous data, summary statistics will include the arithmetic mean, arithmetic standard deviation (SD), median, min, max and N; for log-normal data (e.g. the PK parameters: area under the concentration versus time curve [AUC] and maximum observed drug concentration [C_{max}]) the geometric mean and geometric coefficient of variation (CV%) will also be presented. For categorical data, frequency count and percentages will be presented. Data listings will be provided for all subjects up to the point of withdrawal, with any subjects excluded from the relevant population highlighted. Summary statistics and statistical analyses will generally only be performed for subjects included in the relevant analysis population. For the calculation of summary statistics and statistical analysis, unrounded data will be used.

Mean change from baseline is the mean of all individual subjects' change from baseline values. Each individual change from baseline will be calculated by subtracting the individual subject's baseline value from the value at the timepoint. The individual subject's change from baseline values will be used to calculate the mean change from baseline using a SAS procedure such as Proc Univariate.

Data analysis will be performed using SAS® Version 9.4 or greater.

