12. CHANGES FROM THE PROTOCOL SPECIFIED STATISTICAL ANALYSES

There were no changes from the protocol specified statistical analyses.

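### The SAP reduces pupillometry (and neurological examination) to listings, although the protocol promises descriptive summaries and SAP Section 12 declares no changes

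*SAP*

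**What the plan says.** The protocol makes the commitment twice. The synopsis, under Statistical Analysis, states: "Safety parameters, including safety laboratory, vital signs, neurologic examination, and pupillometry, will be listed and summarized using standard descriptive statistics". Section 10.3.1.2 names the same four groups of safety parameters and adds: "The parameters will be listed, and summarized using standard descriptive statistics". It then exempts ECG and physical examination by name from both listing and summary.

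The SAP plans less. All of Section 9.4.11 reads: "Pupillometry data will be listed for all subjects by treatment and timepoint". Section 9.4.10 asks for new or worsened neurological abnormalities to be reported as AEs, and for the rest says: "Neurological examination data will be listed for all subjects by treatment and timepoint".

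Three other SAP statements govern how these sections are read:
- Section 9.1: "Summary statistics and statistical analysis will only be presented for data where detailed in this SAP".
- Section 3: "This SAP supersedes the statistical considerations identified in the protocol; where considerations are substantially different, they will be so identified".
- Section 12: "There were no changes from the protocol specified statistical analyses".

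**The concern.** Protocol Section 3.3 explains why pupillometry is in the study. Because compounds acting on this pathway could affect sympathetic function, "this study will monitor for evidence of sub-clinical effects on autonomic function using pupillometry". A sub-clinical effect is, almost by definition, one that a subject would not report and an investigator would not normally record as an adverse event. It would be expected to show as a modest shift in group means by dose against placebo, and a descriptive table by treatment and timepoint is the natural place to see that. If the SAP is followed as written, no planned output shows it.

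The second issue is documentary. A reader who relies on Section 12 would conclude that the protocol's safety summaries are all still planned. They are not.

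**Working it through.** No statistical calculation applies; the check is a comparison of texts plus a count of what is left without a summary.

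**Step 1. Protocol against SAP.**

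| Assessment | Protocol synopsis and 10.3.1.2 | SAP |
|---|---|---|
| Vital signs | List and summarize | Summarized with change from baseline and figures, and listed (9.4.4) |
| Chemistry, hematology | List and summarize (as safety laboratory) | Summarized and listed (9.4.3) |
| Urinalysis | List and summarize (a safety laboratory test in Appendix 2) | Listed only (9.4.3) |
| Neurological examination | List and summarize | Listed only (9.4.10) |
| Pupillometry | List and summarize | Listed only (9.4.11) |
| ECG | Neither, stated explicitly | Not presented (9.4.5) |

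The ECG row matters because it shows that the protocol authors chose which assessments to leave out, and pupillometry was not one of them.

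**Step 2. Could a general rule restore the summary?** SAP 9.1 sets out which statistics to give for continuous data, but the same section allows summaries only where the SAP details them. Where the SAP wants a summary it says so, including for the exploratory skin biomarkers (9.4.12) and serum NGF (9.4.13). A section that says only that data are listed therefore means listing only.

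**Step 3. Is the difference declared?** Section 12 says there were no changes. The SAP cites the protocol version dated 04 November 2019. The Amendment (a) summary records no change to protocol Section 10.3.1.2, so a version difference is unlikely to be the explanation.

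**Step 4. Is there another route to a table?**
- Neurological examination: protocol 9.4.4.1 and SAP 9.4.10 direct new or worsened abnormalities to AE reporting, and SAP 9.4.1 tabulates treatment-emergent AEs.
- ECG: clinically significant findings are likewise reported as AEs (protocol 9.4.3, SAP 9.4.5).
- Pupillometry: neither protocol 9.4.4.2 nor SAP 9.4.11 states such a rule.

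**Step 5. Size.** Protocol 9.4.4.2 names 8 measures: maximum diameter, minimum diameter, percentage change, latency, constriction velocity, maximum constriction velocity, dilation velocity and time to 75% recovery. SAP 9.4.11 plans a summary for 0 of the 8. With 6 active and 2 placebo subjects in each of 7 cohorts (SAP Section 5), the planned numbers are:
- LY3478006: 7 × 6 = 42
- Placebo: 7 × 2 = 14, of which 6 × 2 = 12 IV and 1 × 2 = 2 SC
- Total: 42 + 14 = 56, matching the planned number of completers.

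**Step 6. Baseline.** The Schedule of Activities places the predose pupillometry on Day -1 and shows none on Day 1. The Day 1 predose baseline that the SAP uses for vital signs would not work here.

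**The case against.** The mismatch in wording is not in dispute. The case on the other side is that it matters little, because a group-level pattern has several other chances of being noticed:
- Pupillometry is part of the minimum safety data reviewed before each escalation (protocol 7.4.1).
- The sponsor team is unblinded when it reviews safety data before Cohorts 6 and 7 (protocol 10.3.4).
- A safety issue that needs group-level unblinding leads to further analyses (protocol 9.4.5).
- Protocol 10.3.1.2 and SAP Section 3 both leave room for additional analyses.
- The general AE definition in protocol Appendix 1 covers any unfavorable and unintended sign, so a clinically notable pupillometry abnormality could be recorded as an AE.

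In addition, no safety inference is planned (SAP 9.4.15), each dose has about 6 active subjects, and a simple table could be built from the listing at any time. SAP Section 3 requires differences to be identified only if they are substantial, which is a judgement. The TFL shells, which might contain a table, were not available.

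Much of this stands as a limit on the consequence: the gap is in reporting, not in safety oversight. It does not remove the gap. The reviews and extra analyses serve dose decisions or depend on someone having already noticed a signal; none is a planned summary across doses and placebo for the study report. The AE route works one subject at a time and would miss a small shift across a group. Whether or not the difference counts as substantial, the flat statement in Section 12 is inaccurate. If a shell does contain the table, SAP 9.4.11 should say so, because 9.1 ties summaries to the SAP text.

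**Conclusion.** The concern holds. The SAP drops a descriptive summary to which the protocol commits, for the one measure included specifically to look for sub-clinical autonomic effects, and Section 12 wrongly reports no change. The neurological examination omission is the same kind of error with less consequence, because abnormal findings are directed to the AE tables. Urinalysis is a minor further instance.

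The size is limited. The primary endpoint (frequency of SAEs and TEAEs) is unaffected, every pupillometry value would still be listed by treatment and timepoint, and no inference is lost because none was planned. What is lost is any planned view of the 8 pupillometry measures by dose against placebo. It should be fixed, but it does not threaten the study's main conclusions.

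The conclusion rests on two assumptions: that the unseen TFL shells follow the SAP text, and that sub-clinical pupillary changes would not usually be reported as AEs. The second is a reasonable inference, not something the documents state.

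**What to change.** 1. **SAP 9.4.11.** Replace the text with wording such as: *All measures named in protocol Section 9.4.4.2 will be listed, and will be summarized with standard descriptive statistics for each treatment at each scheduled timepoint.* Change from baseline would be a useful addition, though the protocol does not require it; if added, define baseline as the Day -1 assessment.
2. **SAP 9.4.10.** Either add a simple frequency table of neurological findings by treatment, or keep the listing and justify it in Section 12 on the ground that new or worsened abnormalities are reported as AEs.
3. **SAP Section 12.** Correct the statement so that it records every remaining departure from protocol 10.3.1.2, including the listing-only treatment of urinalysis.

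Declaring and justifying listing-only presentation of pupillometry in Section 12 would also remove the inconsistency between the documents. It would still leave no planned summary of the measure, so adding the table is preferable.

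The cost is SAP wording and a few descriptive tables from data already being collected. No new procedures or visits are needed.

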9.4.12 Biomarkers

Abdomen skin biopsy samples will be collected to study protein biomarkers, including tTrkA and pTrkA. The protein biomarkers data will be summarized by ethnicity (overall, Japanese and Non-Japanese) and treatment and listed.

Eli Lilly is responsible for the biomarkers statistical analysis and reporting of data.

9.4.13 Serum NGF levels

Serum NGF levels will be evaluated over time to assess changes in NGF levels and will be listed by subject.

Summary tables, with changes from baseline where baseline is defined as the Day 1 predose assessment, mean (+ SD) figures, overlaying individual figures will be provided for the serum NGF levels by ethnicity (overall, Japanese and Non-Japanese).

Eli Lilly is responsible for the serum NGF levels statistical analysis and reporting of data.

9.4.14 Other assessments

All other safety assessments not detailed in this section will be listed but not summarized or statistically analyzed.

9.4.15 Safety and Tolerability Statistical Methodology

No inferential statistical analyses are planned.

10. Data Review During the Study

Data will be reviewed during the study to evaluate the safety and PK of LY3478006, inform dose selection/escalation decisions, and confirm inclusion of data from an adequate number of Japanese and non-Japanese subjects.

Interim data reviews are planned as follows:

- Prior to initiating the planned **CCI** SC dose level cohort (Cohort 7), it will include
 - PK and safety data from Cohorts 1, 2, and 3 (**CCI** [REDACTED])
- Prior to initiating the **CCI** dose cohort (Cohort 6), or a SC dose level cohort (Cohort 7), it will include:
 - PK data from Cohorts 1, 2, 3, and 4 (**CCI** [REDACTED])
 - Available safety data from Cohorts 1, 2, 3, 4, and 5 (**CCI** [REDACTED])
Safety data from Cohort 5 will not be required for the **CCI** SC dose level cohort (Cohort 7) decision.

11. INTERIM ANALYSES

No interim statistical analyses are planned.

12. CHANGES FROM THE PROTOCOL SPECIFIED STATISTICAL ANALYSES

There were no changes from the protocol specified statistical analyses.

14. DATA PRESENTATION

14.1 Derived Parameters

Individual derived parameters (e.g. PK parameters) and appropriate summary statistics will be reported to three significant figures. Observed concentration data, e.g. C_{max} , should be reported as received. Observed time data, e.g. t_{max} , should be reported as received. N and percentage values should be reported as whole numbers. Median values should be treated as an observed parameter and reported to the same number of decimal places as minimum and maximum values.

14.2 Missing Data

Missing data will not be displayed in listings.

14.3 Insufficient Data for Presentation

Some of the TFLs may not have sufficient numbers of subjects or data for presentation. If this occurs, the blank TFL shell will be presented with a message printed in the center of the table, such as, "No serious adverse events occurred for this study."

Leo Document ID = e38fe50c-6990-423a-8d37-569ab9ce8b6c

Approver: PPD

Approval Date & Time: 10-Jan-2020 14:10:24 GMT

Signature meaning: Approved

Approver: PPD

Approval Date & Time: 10-Jan-2020 14:24:24 GMT

Signature meaning: Approved

Approver: PPD

Approval Date & Time: 21-Jan-2020 19:12:26 GMT

Signature meaning: Approved
